2.2 STUDY OBJECTIVES

The study will generate clinical data on the characteristics of adv/mUC patients treated with avelumab and on the effectiveness and safety of avelumab in the real-world setting.

Primary objective:

To estimate Overall Survival (OS) of adv/mUC patients treated with avelumab in the real-world setting.

Secondary objectives:

- *To describe patients’ characteristics: ECOG (0-4) at ChT 1st and avelumab initiation, sex, age, ChT regimens received in 1st line (Cis/Gem, Carbo/Gem, Cis/Carbo/Gem, MVAC regimens, others), median number of ChT cycles received in 1st line, median time from the end of ChT 1st line to the start of avelumab, best response to 1st line chemotherapy (CR, PR, SD; CR-RP, SD), site and histology of the primary tumor (bladder, urethra or upper tract), site of baseline metastasis before ChT and avelumab (visceral vs non-visceral), biological abnormalities (neutropenia, lymphopenia, impaired renal function, anemia), PD-L1 status and FGFR abnormality, Bajorin risk classification (0, 1, 2) evaluated before the start of ChT 1st line, use of concomitant treatments (corticosteroids/anti-inflammatory steroids (AIS)/non-steroidal anti-inflammatory drugs (NSAIDs), angiotensin-II-receptor antagonists (sartans)/angiotensin-converting enzyme (ACE) inhibitors ,*

PFIZER CONFIDENTIAL

CT24-WI-GL03-RF02 2.0 Non-Interventional Statistical Analysis Plan For Primary Data Collection Study

01-Jun-2020

Page 9 of 28

antibiotics, proton pump inhibitors (PPI)) at avelumab initiation, type of neoadjuvant and adjuvant treatments.

- *To estimate: Overall Survival from the start of ChT in 1st line, Progression Free Survival one and two (PFS1 and PFS2). Overall Response Rate (ORR), Duration of Response (DOR) and Duration of Treatment (DOT) while receiving avelumab.*
- *To describe the pattern of progression while receiving avelumab.*
- *To describe subsequent treatments and response to these treatments.*
- *To describe the safety profile of avelumab.*
- *To describe use of premedication (acetaminophen and antihistamine).*
- *To describe Patient-Reported Outcomes (PROs) related to symptoms via the NCCN/FACT FBISI-18 questionnaire and related to global health via the EQ-5D-5L questionnaire. This objective will be evaluated only among patients initiating avelumab after the start of the study.*

3 INTERIM ANALYSES

A first interim analysis (IA1) will be performed for the population of participants who begun avelumab at least 6 months before the cut-off date of 31 January 2022 (Abstract for ESMO 2022 with associated publication) and then every year for publication purposes.

For the IA1, all efficacy and safety analyses will be presented for this population (8.2) and depending on the maturity of the data at least demographic/baseline characteristics data (8.2.4), time-to-event analyses and safety data (8.2.3) on the whole population (SAF population for safety analyses and FAS population otherwise). Subgroup analyses may be performed depending on the maturity of data and medical interest.

4 HYPOTHESES AND DECISION RULES

4.1 STATISTICAL HYPOTHESES

There are no formal statistical hypotheses for this study.

4.2 STATISTICAL DECISION RULES

All the analyses will be purely descriptive. Two-sided 95% confidence interval will be provided for estimates of primary interest.

5 ANALYSIS SETS/POPULATIONS

5.1 FULL ANALYSIS SET

The full analysis set (FAS) is defined as all enrolled participants who received at least one injection of avelumab. "Enrolled" means a participant, or his or her legally authorized representative's, agreement to participate in a clinical study following completion of the informed consent/assent process and who meet all eligibility criteria. Potential participants who are screened for the purpose of determining eligibility for the study, but do not participate in the study, are not considered enrolled.

PFIZER CONFIDENTIAL

CT24-WI-GL03-RF02 2.0 Non-Interventional Statistical Analysis Plan For Primary Data Collection Study

01-Jun-2020

Page 10 of 28

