## 9. RESEARCH METHODS

### 9.1. Study design

Multicenter ambispective (retrospective and prospective) non-interventional study of adv/mUC patients treated with avelumab, not impacting the treatment decision made by the treating physician and the medical management of treated patients (Figure 1).

Inclusion period: expected 18 months to reach sample size.

Target sample size is 600 patients.

- All patients who initiated avelumab before the start of the study in the site will be included retrospectively. All patients are eligible: those under avelumab at inclusion, those who died before the start of the study, and those no longer treated with avelumab at the time of the study start.
- Patients initiating the drug after the start of the study in the site will be prospectively included.

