### 9.2.1. Inclusion criteria

Patients must meet all of the following inclusion criteria to be eligible to the study:

1. Patient  $\geq 18$  years of age
2. Patient with locally advanced or metastatic urothelial carcinoma (irrespective of tumor histology) whose disease has not progressed (ongoing stable disease, partial response or complete response) following completion of first-line platinum-based chemotherapy and who has been (retrospective), is (retrospective and prospective), will be (prospective) treated with avelumab.
3. For a patient alive at the moment of the inclusion in the study : the patient must be informed of the study, he/she must be given an information letter signed by the investigator and must not be opposed to the collection of his/her data

For a patient who died before the inclusion in the study : the patient (during his lifetime) must not be opposed in writing to the collection of his data. 4. Patient benefiting from a social security scheme according to local regulations

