### 9.7. Data analysis

A detailed statistical analysis plan will be available before the database lock.

All effectiveness analyses (except PRO analysis) will be performed on a Full Analysis Set (FAS) defined as all enrolled patients who received at least one injection of avelumab. "Enrolled" means a participant's, or his or her legally authorized representative's, agreement to participate in a clinical study following completion of the informed consent/assent process and who meet all eligibility criteria. Potential participants who are screened for the purpose of determining eligibility for the study, but do not participate in the study, are not considered enrolled.

The primary end point is the Overall Survival (OS). OS is defined as the time from the date of first injection of avelumab to the date of death due to any cause. Patients last known to be alive will be censored at date of last contact. OS will be summarized using the Kaplan-Meier method and displayed graphically. Confidence intervals (CIs) for the 25th, 50th (median) and 75th percentiles will be reported. In particular, six-months and one-year survival rate will be assessed with a 95%CI.

A first interim analysis (IA) will be performed 6 months after the inclusion of the 1st patient and then every year for publication purposes.

The data collected in the present study may also be analyzed together with data from other countries, to increase sample size to address with a higher precision some of the study objectives. The details of this pooled analysis will be described in a separate analysis plan.

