#### Patients selection

In order to limit the selection bias of study patients, participating centers will be asked to include retrospectively all eligible patients from their center who had already initiated a treatment with avelumab for adv/mUC, and for the prospective part of the study, to consecutively enroll all eligible patients after study set-up, until the planned number of patients have been included in the study. All patients who died before study set-up will be included, to avoid survival bias.

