## 10.2. Patient consent

The informed consent documents and any patient recruitment materials must be in compliance with local regulatory requirements and legal requirements, including applicable privacy laws.

In the present French study, no signed consent is required. An information note signed by investigator is provided to the patient.

The informed consent documents used during the informed consent process and any patient recruitment materials must be reviewed and approved by Pfizer, approved by the institutional review board (IRB)/independent ethics committee (IEC) before use, and available for inspection.

The investigator must ensure that each study patient or his or her legally acceptable representative, is fully informed about the nature and objectives of the study, the sharing of data relating to the study and possible risks associated with participation, including the risks associated with the processing of the patient's personal data. The investigator further must ensure that each study patient or his or her legally acceptable representative, is fully informed about his or her right to access and correct his or her personal data and to withdraw consent for the processing of his or her personal data.

Whenever consent is obtained from a patient's legally acceptable representative, the patient's assent (affirmative agreement) must subsequently be obtained when the patient has the capacity to provide assent, as determined by the IRB/IEC. If the investigator determines that a patient's decisional capacity is so limited that he or she cannot reasonably be consulted, then, as permitted by the IRB/IEC and consistent with local regulatory and legal requirements, the patient's assent may be waived with source documentation of the reason assent was not obtained. If the study patient does not provide his or her own consent, the source documents must record why the patient did not provide consent (e.g., minor, decisionally impaired adult), how the investigator determined that the person signing the consent was the patient's legally acceptable representative, the consent signer's relationship to the study patient (e.g., parent, spouse), and that the patient's assent was obtained or waived. If assent is obtained verbally, it must be documented in the source documents.

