8.2.1 Primary criterion analyses

The primary criterion is the Overall Survival, evaluated in the FAS.

This criterion will be analyzed using the Kaplan-Meier method and survival curves will be presented. The starting date to be used is the date of first intake of study treatment.

The censoring and event date options to be considered for the OS analysis are defined as follows:

PFIZER CONFIDENTIAL

CT24-WI-GL03-RF02 2.0 *Non-Interventional Statistical Analysis Plan For Primary Data Collection Study*

01-Jun-2020

Page 17 of 28

Table 1: Event Date and Outcome for Overall Survival

Scenario	Date of Event/Censoring	Outcome
Death during study	Date of death	Event
Death after treatment discontinuation	Date of death	Event
Alive	Date of last contact	Censored
Lost to follow-up	Date of last contact	Censored

OS will also be described by subgroup (See section 5.3 for subgroup definition).

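### The FAS rule for primary OS rests on a consent-process agreement that patients who died before inclusion cannot give, which contradicts the design's deliberate inclusion of those deaths

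*SAP*

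**What the plan says.** **Analysis set.** SAP 8.2.1: "The primary criterion is the Overall Survival, evaluated in the FAS". SAP 5.1: "The full analysis set (FAS) is defined as all enrolled participants who received at least one injection of avelumab". The next sentence of SAP 5.1 explains enrolment as the participant's, or a legally authorized representative's, "agreement to participate in a clinical study following completion of the informed consent/assent process and who meet all eligibility criteria". Protocol 9.7 has the same rule ("defined as all enrolled patients who received at least one injection of avelumab") and the same explanation, and applies it to every effectiveness analysis except PRO. Neither document therefore overrides the other.

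**Design.** Protocol 9.1 lists as eligible "those who died before the start of the study, and those no longer treated with avelumab at the time of the study start"; the protocol abstract and SAP 2.1 agree. Protocol 9.9.1 gives the reason: "All patients who died before study set-up will be included, to avoid survival bias".

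**Entry rule for deceased patients.** Protocol 9.2.1, criterion 3: "the patient (during his lifetime) must not be opposed in writing to the collection of his data". Protocol 9.2 has families of deceased ATU patients informed. SAP 2.1 has the person of trust informed. In neither place is anyone asked to agree on the patient's behalf.

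**Consent in general.** Protocol 10.2: "In the present French study, no signed consent is required". The investigator signs an information note instead.

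**The concern.** The enrolment definition joins two conditions with an 'and': agreement after a consent or assent process, and all eligibility criteria. A patient who died before inclusion can meet the second but not the first. Non-opposition might pass as agreement for a living patient who has received the information letter. It cannot for someone who died before any study information could be given.

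A programmer who follows the definition to the letter would therefore leave these patients out of the FAS. Retrospective patients alive at inclusion would stay in and be counted from their first injection, so time they had to survive in order to be included would count as follow-up at risk. That is the survival bias that Protocol 9.9.1 sets out to prevent. Nothing in the primary analysis would correct it: SAP 8.1.3 and 8.2.2.1 plan left truncation only for OS from the start of chemotherapy, with avelumab start as the entry time. PFS, ORR, DOR and DOT use the same set. The safety set in SAP 5.2 has no agreement condition, so the same deaths could count for safety and not for effectiveness.

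**Working it through.** **1. The texts side by side**

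| Question | Rule | Can a patient deceased before inclusion meet it? |
|---|---|---|
| Eligible? | Protocol 9.1, 9.2.1; SAP 2.1 | Yes, named explicitly |
| To be included? | Protocol 9.9.1 | Yes, on purpose |
| Enrolled? | Protocol 9.7; SAP 5.1: agreement after consent or assent, and eligibility | No route is provided |
| In the FAS? | Enrolled and at least one injection | No, on the literal reading |
| In the safety set? | SAP 5.2: at least one injection | Yes |

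**2. The plan's own figure**

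Protocol 9.5 gives an exponential model with mean 29 months, n = 600 and a two-sided 95% CI of 18.6 to 21.8. The exact limits are 2nm/χ²(0.975; 2n) and 2nm/χ²(0.025; 2n), with m = 29 × ln 2 = 20.10:

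- Lower: 1200 × 20.10 / 1297.9 = 18.59.
- Upper: 1200 × 20.10 / 1105.9 = 21.81.

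The figure is reproduced. With m exactly 20, the limits are 18.49 and 21.70.

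**3. Effect of the literal reading**

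From the protocol: median 20 months, so λ = ln 2 / 20 and 1/λ = 28.85 months; no censoring before the median. Assumed, because the documents do not say: a share f of the cohort is retrospective, and the gap from first dose to inclusion is uniform on 0 to L months.

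- Probability that a retrospective patient died before inclusion: p = 1 − (1 − e^(−λL)) / (λL). This gives 0.097 for L = 6, 0.141 for L = 9 and 0.182 for L = 12.
- Fraction of the cohort kept: D = 1 − f·p.
- For t ≥ L, a retrospective patient is alive at t, and so was alive at inclusion, with probability e^(−λt). Kaplan-Meier without delayed entry therefore tends to e^(−λt)/D.
- Apparent median: 20 + 28.85 × (−ln D).

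| f | L (months) | D | Dropped of 600 | Apparent median (months) | 12-month OS (true 66.0%) |
|---|---|---|---|---|---|
| 25% | 6 | 0.976 | 15 | 20.7 | 67.6% |
| 50% | 6 | 0.951 | 29 | 21.4 | 69.3% |
| 25% | 12 | 0.955 | 27 | 21.3 | 69.1% |
| 50% | 12 | 0.909 | 55 | 22.8 | 72.6% |

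Example, last row: D = 1 − 0.5 × 0.182 = 0.909; −ln D = 0.0953; 20 + 28.85 × 0.0953 = 22.75.

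Larger values give more: f = 70% with L = 16 gives 25.1 months.

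**4. Values closer to the documents' calendar**

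ATU use began in July 2020, data collection was planned for Q2 2021 (9 to 12 months later), and inclusion was expected to take 18 months. With constant uptake, the retrospective share is 9/27 = 33% to 12/30 = 40%.

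- 33%, L = 9: D = 0.953, median 21.4.
- 40%, L = 12: D = 0.927, median 22.2.

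These lie on either side of the planned upper limit of 21.8. Rising uptake would reduce the shift; late site opening would increase it.

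**5. Precision**

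With 545 patients left (50%, 12 months), the interval in step 2 is 3.39 months wide against 3.23 with 600. The issue is bias, not precision.

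**The case against.** The strongest reply is that the plan, read as a whole, puts these deaths in. Several sections name them as eligible, Protocol 9.9.1 requires their inclusion and says why, and criterion 3 gives them their own entry rule. The sentence after the enrolment definition only separates patients who were screened but did not take part. The wording looks like interventional-trial text that was not adapted. Protocol Table 2 lists eligibility criteria and the date the information letter was provided, but no consent or agreement date, so the natural FAS flag is eligibility plus one injection, which keeps the deaths. The study is also purely descriptive (SAP 4.1 and 4.2).

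Most of this stands, and it rules out two stronger readings. A reader might infer that early deaths are being lost and that primary OS is biased. The documents do not show this: the design text points the other way, and no instruction tells the analyst to filter on consent. A reader might also infer that consent has no place in this study. That goes too far: Protocol 9.2.2 refers to oral consent, 10.2 describes a consent process, and the reporting-period text in 11.2 uses the time of informed consent.

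The reply does not remove the contradiction. The FAS definition is the operative rule for the primary set, it appears in both documents, and no sentence exempts deceased patients. The allowance for a legally authorized representative does not help, because neither document provides for such agreement on behalf of someone already dead. SAP 8.2.4 reports patients excluded from the analyses with reasons, so the wording of the set decides who is counted there.

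**Conclusion.** The concern holds as a contradiction between the analysis-set rule and the design, present in the current text of both documents. Confidence is high that the wording conflicts and that a literal application would overstate OS. Confidence in the size is low, because it rests on the exponential model in Protocol 9.5 and on an assumed retrospective share and gap. Over the cases in the table the median would rise by 0.7 to 2.8 months. The calendar-based cases straddle the planned upper limit, so a reader should not infer that the shift would necessarily exceed the plan's precision. If the deaths are kept, as the design intends, there is no shift and the planned figure is unchanged. This should be fixed, but it is not an established flaw in the results.

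**What to change.** In SAP 5.1, replace the consent-based explanation of enrolment. Define the FAS as all included patients who meet the Protocol 9.2 criteria (non-opposition if alive at inclusion; no written opposition if deceased before inclusion) and who received at least one avelumab injection. State explicitly that patients deceased before inclusion are in the FAS, and report their number with the participant flow in SAP 8.2.4. Align Protocol 9.7 at the next amendment.

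Aligning criterion 3 in SAP 2.1 with the protocol would not be enough, because the enrolment definition would remain.

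Cost: a SAP revision and no new data. The protocol change needs the usual ethics committee (CPP) authorization under Protocol 10.4, which is why it can wait for the next amendment while the SAP is corrected first. The looser consent wording in Protocol 9.2.2, 10.2 and 11.2 would remain, but it does not determine the analysis set.

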5.2 SAFETY ANALYSIS SET

The safety analysis set (SAF) is defined as all participants who received at least one injection of avelumab.

5.3 SUBGROUPS

The primary and secondary objectives will be evaluated on the overall population and for prespecified subgroup.

- Main subgroup of interest: histology (UC with variant; UC without variant).
- Other subgroups of interest:
 - Histology (Pure UC; UC with variant, Pure adenocarcinoma, Other, Missing)
 - ECOG at avelumab initiation (PS 0-1; PS ≥ 2),
 - Locally advanced urothelial carcinoma versus metastatic urothelial carcinoma,
 - Previous ChT regimens (Cis/Gem, Carbo/Gem, Cis/Carbo/Gem, MVAC regimens, others),
 - Best response to 1st line chemotherapy (CR, PR, SD)
 - Regrouped best response to 1st line chemotherapy (CR+PR, SD),
 - Number of ChT cycles received in 1st line (< 4 cycles; ≥ 4 cycles and ≤ 6 ; > 6 cycles), Site of baseline metastases before ChT (visceral vs non-visceral),
 - Participants with an early relapse on avelumab and participants with a long-term response to avelumab. Patient is considered as early progressor if PFS is less than 3 months and if progression is observed. Patient is considered as long responder if PFS is equal or higher than 12 months, whatever the outcome.
This subgroup of interest will be used only for Overall Survival and progression free survival analyses, and baseline characteristics.
 - Delay between the end of ChT and the start of avelumab (< 4 weeks; between 4 and 10 weeks; > 10 weeks),
 - Delay between the end of ChT and the start of avelumab (< 4 weeks; ≥ 4 weeks),
 - ATU participants versus non ATU participants, site for the primary tumor (bladder, urethra, upper tract),
 - PD-L1 status,
 - FGFR abnormality,
 - Bajorin risk classification evaluated before ChT 1st line (0, 1, 2),
 - Presence of biological anomalies (neutropenia, lymphopenia, impaired renal function, anemia),
 - Use of concomitant treatments (corticosteroids/AIS/NSAIDs, sartans/ACE inhibitors, antibiotics, PPI) at avelumab initiation,
 - Type of subsequent treatment: Antibody-Drug Conjugate (ADC) treatment, chemotherapy, immunotherapy, targeted therapy, other. This classification will be made thanks to a medical review from Pfizer team.
 - Type of subsequent treatment: ADC versus Other.

PFIZER CONFIDENTIAL

CT24-WI-GL03-RF02 2.0 Non-Interventional Statistical Analysis Plan For Primary Data Collection Study

01-Jun-2020

Page 11 of 28

Analysis in subgroups will be discussed in function of the number of participants in each subgroup. If too few people are in each subgroup (less than 10 participants), no analysis will be conducted for the corresponding subgroups.

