8.1.3 Analysis of time-to-event data

Kaplan-Meier estimates (product-limit estimates) will be presented together with a summary of associated statistics including the median survival time with 2-sided 95% CIs. In particular, the survival rate at 3, 6, 9, 12, 15, 18 and 24 months will be estimated with corresponding 2-sided 95% CIs. The CIs for the median will be calculated according

PFIZER CONFIDENTIAL

CT24-WI-GL03-RF02 2.0 *Non-Interventional Statistical Analysis Plan For Primary Data Collection Study*

01-Jun-2020

Page 15 of 28

to Brookmeyer and Crowley (Brookmeyer R, 1982) and the CIs for the survival function estimates at the time points defined above will be derived using the log-log transformation according to Kalbfleisch and Prentice (Kalbfleisch JD, 2002) (conftype=loglog default option in SAS Proc LIFETEST) with back transformation to a CI on the untransformed scale. The estimate of the standard error will be computed using Greenwood's formula.

Frequency (number and percentage) of participants with each event type and censoring reasons will be presented.

For each subgroup analysis, comparison of the different modalities to a reference level will be performed using univariate Cox proportional hazard models. Ties will be handled using the Exact option in SAS (Ties=Exact option in SAS PROC PHREG). Results will be expressed in terms of hazard ratios (HR) and a 2-sided 95% CI will be associated to each HR. A HR of 1 equals a lack of association, a HR greater than 1 suggests an increased risk compared to the reference level, and a HR below 1 suggests a decreased risk.

Time of follow-up for each event (OS and PFS)

A Kaplan-Meier estimation for follow-up duration will also be generated to assess the follow-up time reversing the censoring and event indicators.

Handling of left truncation and right censoring:

The overall survival from the first injection of the chemotherapy used in 1st line will cover

a retrospective and/or prospective data collection period. The time to event of interest ("survival" time) or censoring if no event occurs (right censoring) will be based on the 1st line of chemotherapy start date at a time-point preceding the study entry (avelumab start date). As a result, only participants who are still alive are included in the study.

Therefore, the time from 1st line of chemotherapy start date to avelumab start date is called immortal time and corresponds to a left truncation in survival analyses.

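### OS and PFS from avelumab start are compared between groups defined by later PFS: the OS hazard ratio is partly built in, the PFS one cannot be estimated, and OS by subsequent treatment is conditionally affected

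*SAP*

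**What the plan says.** SAP 5.3 defines two outcome-based groups. The first: "Patient is considered as early progressor if PFS is less than 3 months and if progression is observed". The second: "Patient is considered as long responder if PFS is equal or higher than 12 months, whatever the outcome". It then sets their use: "This subgroup of interest will be used only for Overall Survival and progression free survival analyses, and baseline characteristics". The same list contains type of subsequent treatment, once in five categories and once as "Type of subsequent treatment: ADC versus Other", with no limit on the endpoints concerned.

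For OS, SAP 8.2.1 states: "The starting date to be used is the date of first intake of study treatment". It adds a description by the 5.3 subgroups without exception. SAP 8.2.2.2 does the same for PFS, with the same time zero. SAP 8.1.3 fixes the method: "For each subgroup analysis, comparison of the different modalities to a reference level will be performed using univariate Cox proportional hazard models", with a 95% CI for each hazard ratio. No landmark, time-dependent covariate or delayed entry is planned for these groups.

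Two other texts bear on the point.

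- The summary table in SAP 8.2.5 refers to 5.3 for OS only. It shows no subgroups for PFS, and it names progression status and subsequent-treatment category only for baseline or safety tables.
- Protocol Section 8 prespecifies comparable groups with different definitions: progression at the first tumour assessment, and the fourth quartile of response to avelumab.

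**The concern.** Membership of these groups is decided after time zero. PFS counts death as an event (SAP 6.1.1), so a patient with PFS of 12 months or more was alive at month 12. The long-responder OS curve therefore stays at 100% for a year by definition, while early progressors can die in that year. A Cox model from the first dose reads this as a lower hazard.

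For PFS, the grouping variable is the outcome itself.

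For type of subsequent treatment, a patient must survive to the start of that treatment to be classified, so each group's OS curve from avelumab start includes survival that was guaranteed.

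At stake is a table or figure that appears to show a clear survival advantage on the primary endpoint when some or all of it follows from the definition. The SAP already applies the relevant principle elsewhere. It names immortal time and uses left truncation for OS from chemotherapy start (8.1.3, 8.2.2.1), and it starts OS of subsequent treatment at that treatment (8.2.2.8).

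**Working it through.** **Inputs from the documents.** Exponential OS with median 20 months, 600 patients, two-sided 95% CI (protocol 9.5); 18 months of inclusion and 24 months of follow-up after the last inclusion (protocol 9.1); group definitions and Cox method as above. Median PFS and start times of subsequent treatment are not given, so ranges are assumed.

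**The plan's own figure.** The CI for an exponential median M is 2nM/χ²(0.975; 2n) to 2nM/χ²(0.025; 2n). With the protocol's mean of 29, M = 29 × ln 2 = 20.1. For n = 600 this gives 18.59 to 21.81 (stated: 18.6 to 21.8). For n = 47 it gives 15.40 to 27.36 (stated: 15.4 to 27.4). Both reproduce.

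**OS by early/long status when there is no association.** The death hazard is constant at ln 2/20 = 0.0347 per month and does not change at progression. The progression hazard is ln 2/(median PFS) − ln 2/20. Censoring is uniform over 24 to 42 months. The expected long-responder share is 0.5^(12/median PFS), for example 0.5^(12/6) = 25%. Medians and hazard ratios come from 400,000 simulated patients, and the last column from 1,000 simulated studies of 600.

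| Assumed median PFS | Early / long per 600 | Median OS early / long (months) | OS HR long vs early | HR from a 12-month landmark | 95% CI excludes 1 |
|---|---|---|---|---|---|
| 4 months | 195 / 75 | 21.3 / 32.1 | 0.57 | 1.00 | 90% |
| 6 months | 123 / 150 | 21.3 / 32.1 | 0.56 | 0.99 | 96% |
| 9 months | 68 / 238 | 21.5 / 32.1 | 0.55 | 1.01 | 91% |

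The true hazard ratio is 1 in every row. The long-responder median is simply 12 + 20 = 32 months. OS at 12 months is 100% in long responders, 69% in early progressors, and 0.5^(12/20) = 66% overall.

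**PFS by early/long status.** Every early event falls before month 3, when all long responders are still at risk. Each such event contributes 1/(n_early + n_long × HR) to the partial likelihood, which rises as HR falls to 0. After month 12 only long responders remain and HR cancels from each term. The likelihood is monotone, so the estimate runs to 0 and no finite hazard ratio exists. A middle category would not rescue a contrast with long responders, because its patients also leave the risk set before month 12.

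**OS from avelumab start by type of subsequent treatment.** Same constant death hazard, no treatment effect, and patients classified only if alive and uncensored when treatment starts. Mean start is assumed at 6 months for Other and varied for ADC.

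| Mean start, Other / ADC (months) | 12-month OS, Other / ADC | HR from avelumab start | HR from treatment start |
|---|---|---|---|
| 6 / 6 | 81% / 80% | 1.01 | 1.01 |
| 6 / 8 | 81% / 85% | 0.90 | 0.99 |
| 6 / 9 | 81% / 87% | 0.87 | 1.01 |
| 6 / 12 | 80% / 91% | 0.75 | 1.00 |
| 6 / 15 | 80% / 94% | 0.65 | 1.00 |

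Both curves lie above the true 66% in every row. The hazard ratio is distorted only when start times differ. If the start times were exchanged, 0.75 would become 1/0.75 = 1.33, so the direction is open as well.

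**The case against.** The SAP states no hypotheses and calls all analyses descriptive (4.1, 4.2). These groups are two among many secondary subgroups, and interim subgroup analyses are optional (Section 3). That limits the consequence, but curves, hazard ratios and CIs are still planned, and a descriptive hazard ratio can mislead in the same way.

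The summary table in 8.2.5 could mean that PFS by subgroup is not intended. The text of 5.3 and 8.2.2.2 says that it is. PFS by early/long status is therefore contradictory within the SAP, not settled. OS by the 5.3 subgroups is stated consistently.

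Some stronger readings are tempting but not supported:

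- A reader might infer that the whole OS gap between long and early groups will be artefact. Patients who progress late may truly live longer. The figures above show how large a gap appears with no such difference, not how an observed gap divides.
- A reader might infer that ADC versus Other is biased in favour of ADC. The documents give no start times, so neither the presence, direction nor size of a bias in that hazard ratio is known.
- A reader might picture treated against untreated patients. SAP 5.3 lists only types of treatment and no untreated level.
- A reader might extend the argument to response rate or treatment duration by subsequent treatment. Grouping on later information is questionable there too, but a response proportion contains no immortal time, and this point does not cover those endpoints.

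**Conclusion.** The point holds for OS and PFS by early/long status. For OS, the planned comparison yields a hazard ratio of about 0.55 to 0.57 and medians of about 32 versus 21 months when death is unrelated to progression, and with 600 patients its CI excludes 1 in 90% to 96% of simulated studies. A 12-month landmark returns about 1. This rests on constant hazards, the protocol's 20-month median, censoring at 24 to 42 months and an assumed median PFS of 4 to 9 months; the guaranteed 12 months need none of these assumptions. PFS by the same groups is circular whatever the data.

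For OS from avelumab start by type of subsequent treatment, the curves always include guaranteed survival, while bias in the hazard ratio depends on unequal start times. A reader might infer that the primary result is compromised. It is not: the overall OS estimate and the main histology subgroup do not use these groupings.

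**What to change.** 1. In SAP 5.3 and 8.2.1, replace OS by early/long status with a landmark analysis. For example, at month 12, among patients alive and in follow-up, compare progression-free with progressed patients and count OS from the landmark. State how patients are classified whose PFS was censored at treatment discontinuation before the landmark (8.2.2.2, Table 2), since their progression status at that time is undefined.
2. Delete PFS by early/long status from 5.3 and 8.2.2.2.
3. Compare OS by type of subsequent treatment only from the start of that treatment (8.2.2.8), not from avelumab start.
4. Make 5.3, 8.2.1, 8.2.2.2 and the table in 8.2.5 agree, and reconcile them with the outcome-based groups in protocol Section 8.

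Baseline descriptions by these groups can stay.

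The cost is SAP wording, reconciliation with the protocol definition and a few re-programmed tables. A landmark also drops patients who died or were censored before it. Under the protocol's exponential assumption, deaths alone remove about 600 × (1 − 0.66) = 204 patients by month 12.
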